### 10.8. Questionnaire for Symptoms of Potential Orthostasis (QSO)

Data recorded from the questionnaire for symptoms of potential orthostasis will collect the occurrence of the following symptoms:

- Dizziness (yes/no)
- Fainting (yes/no)
- Fall (yes/no).

For each symptom, information on the following will be collected:

- Severity (mild/moderate/severe)
- Number of times (since last minute)
- Comparison to prior episodes (worse/same/better)

The number of occurrences of each symptom over time will be presented. Severity, for those with each symptom, will be tabulated by visit.

These will be summarized and listed by treatment and visit, as well as ‘at any time’ during double-blind treatment.

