#### **8.3.2.8. Questionnaire for Symptoms Potentially Associated with Orthostasis**

At all visits, a short questionnaire will be used to assess the occurrence of dizziness/lightheadedness, fainting/loss of consciousness and falls. The questionnaire will collect the occurrence of symptoms from a pre-defined checklist of terms as well as the frequency and severity of the symptoms.

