#### **10.8.1. Falls as Reported from QSO**

The rate of falls per month will be analyzed using the data on fall occurrence that is collected at each visit in the Treatment Period via the Questionnaire for Signs of Potential Orthostasis.

Rate of falls per month = (total number of falls / duration (days)) x 30, where:

- Total number of falls = summation of falls over all visits in the Treatment Period (through Week 24)
- Duration of treatment (days) through Week 24 = (last dose date of double blind IP – first dose date of double blind IP) + 1

Incidence rate will be summarized by treatment. The incidence rate will be analyzed using the MMSE model methodology as described for the primary efficacy endpoint but without the ‘visit’ terms.

Additional analysis will be performed for each symptom by treatment, visit and overall

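### The recall period that SAP 10.8 states for symptom counts contradicts the falls-per-month formula in SAP 10.8.1, whose denominator also stops at the last dose and not at the last questionnaire

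*SAP*

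**What the plan says.** SAP 10.8 lists three symptoms (dizziness, fainting, fall). For each it records severity, a comparison with prior episodes, and a count: "Number of times (since last minute".

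SAP 10.8.1 turns the fall counts into a rate, "using the data on fall occurrence that is collected at each visit in the Treatment Period". The formula is "Rate of falls per month = (total number of falls / duration (days)) x 30, where". The numerator is "Total number of falls = summation of falls over all visits in the Treatment Period (through Week 24". The denominator, "Duration of treatment (days) through Week 24", is the last double-blind dose date minus the first, plus one. The rate is then compared between arms with the primary-endpoint model without its visit terms.

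Protocol 8.3.2.8 says that "At all visits, a short questionnaire will be used to assess the occurrence of dizziness/lightheadedness, fainting/loss of consciousness and falls", and that the form records occurrence "as well as the frequency and severity of the symptoms". It gives no recall period. Neither does the schedule (Protocol Table 2) nor the planned analysis in Protocol 10.4.5.5.

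**The concern.** Visit counts add up to a subject's total falls only if the look-back windows join end to end. The one look-back that the documents state for this questionnaire does not reach the previous visit, so SAP 10.8 and 10.8.1 cannot both be right. The same line governs the dizziness and fainting counts. Elsewhere the SAP states a usable recall where one matters: about a month for the CAF and the NEVHI, and the past year or since the previous visit for the C-SSRS. Here the reader has to guess.

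There is a related mismatch at the other end of the formula. Counting stops at the last questionnaire, while the days stop at the last dose. Where these dates differ, falls and days cover different time. They differ mainly in subjects who discontinue, so unequal discontinuation across arms would carry the error into the treatment comparison.

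**Working it through.** The documents give no fall rate or precision target, so there is no figure of the plan's own to reproduce. The check is one of consistency.

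**1. Which recall does the formula need?** Protocol Table 2 places the visits at days 7, 14, 28, 42, 56, 70, 84, 126 and 168. SAP Section 3 records that the Safety Monitoring Committee recommended omitting Visits 5, 7 and 9, which leaves days 7, 28, 56, 84, 126 and 168.

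- Six visits: 7 + 21 + 28 + 28 + 42 + 42 = 168 days.
- Nine visits: 7 + 7 + 14 + 14 + 14 + 14 + 14 + 42 + 42 = 168 days.

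If each questionnaire asks about the time since the last one, the windows cover the whole 24 weeks under either schedule, and summed falls ÷ days × 30 is a proper monthly rate. With any shorter recall, falls in the gaps go uncounted while their days stay in the denominator.

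**2. Do the start points agree?** Yes. The first double-blind dose is taken in the clinic at Baseline (Protocol 8.1), where the questionnaire is also given (Protocol Table 2). SAP 7.7.2 assigns assessments on that date to the run-in, so the Baseline count stays out of the sum.

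**3. Do the end points agree?** Not always. Protocol 6.6.2 asks for the Early Termination Visit preferably within 7 days of stopping study medication, and Table 2 schedules the questionnaire there. SAP 7.7.2 runs the Double-Blind Treatment Period to 7 days after the last dose. A questionnaire in that interval therefore belongs to the Treatment Period, but the days it covers after the last dose are not in the denominator.

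Let D be the days from first to last dose inclusive, and g the days from last dose to last questionnaire. Assume a constant fall rate that does not change on stopping. The formula then returns the true rate times (D + g)/D.

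| Illustration | D | g | Factor |
|---|---|---|---|
| Stops at 28 days | 28 | 7 | 35/28 = 1.25 |
| Stops at 84 days | 84 | 7 | 91/84 = 1.08 |
| Completer, last dose the evening before Week 24 | 168 | 1 | 169/168 = 1.006 |

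The error can also run the other way. Suppose a subject's last questionnaire is at Week 12 (84 days), dosing continues to 126 days, and the subject is then lost without a termination visit. The formula divides 84 days' worth of falls by 126 days, a factor of 84/126 = 0.67. The dropout times here are assumptions for illustration; the documents give none.

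**The case against.** The strongest reply is that this is a typing error and that nobody would run the questionnaire as described. That is very likely true. The form is given one to six weeks apart, the counts are summed over visits, and a comparison with prior episodes is requested; all of this presupposes a look-back between visits. SAP 10.8.1 contains a similar slip, naming an MMSE model where MMRM appears to be meant. The form itself fixes what was collected. If it asks about the time since the last visit, the data are sound and only the parenthesis is wrong.

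The reply also limits the importance. The safety analysis is described as descriptive (SAP Section 10). The fall rate is outside the testing hierarchy (SAP 7.5). Adverse events are reviewed at every visit, with suggested questions about the time since the last visit or contact (Protocol 8.3.2.1.5). SAP 10.1 compares the proportion of patients who fall by a CMH test and may show time to first fall.

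All of that stands. It does not remove the contradiction: the only recall stated for these counts is unusable, and SAP 7.3 gives the SAP precedence over the protocol on analysis. Nor does it answer the denominator mismatch, which remains even if the recall is exactly what one expects.

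**Conclusion.** The SAP text contradicts itself and should be corrected, as a minor point in the safety analysis. It has no effect on the primary or secondary endpoints.

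A reader might infer that falls per month cannot be measured in this trial, or might work out a large understatement from the literal recall or from some short fixed window. The documents do not support either step. Nothing suggests that the literal window was used, no fixed window is mentioned anywhere, and the deciding form is not available. No size can therefore be put on the recall error itself.

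The denominator mismatch can be sized, conditionally: under 1% for a typical completer, and up to 25% in the overstating direction in the 28-day illustration. These figures assume a constant fall rate and a termination questionnaire 7 days after the last dose. The net effect on an arm depends on how many subjects discontinue, when, and whether they attend the termination visit.

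**What to change.** 1. Check the recall period printed on the questionnaire form, then correct SAP 10.8 to match it. The expected wording is: since the last QSO assessment.
2. If the form turns out to use a fixed window shorter than the visit gaps, set the SAP 10.8.1 denominator to the days that the completed questionnaires actually cover.
3. Otherwise, run the denominator in SAP 10.8.1 from the first double-blind dose to the last questionnaire in the Double-Blind Treatment Period, including one at Early Termination, and keep the plus-one convention. This also fits the 7-day rule used for on-treatment adverse events in SAP 10.1.

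Do not change the protocol text or the form for this purpose. The SAP reports that the Safety Monitoring Committee had already met, so the study was under way; a new form could not repair counts already taken and might mix two recall periods.

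The cost is one check of the form and two edited lines in the SAP. If the form asks about the time since the last visit, no further data are needed.

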#### **10.4.5.5. Questionnaire for Signs of Potential Orthostasis**

The incidence of dizziness/lightheadedness, fainting/loss of consciousness and falls will be analyzed using data collected at each visit in the Treatment Period via the Questionnaire for Signs of Potential Orthostasis.

Descriptive summaries of the results from the questionnaire for signs of potential orthostasis will be presented separately for each study visit and treatment group.

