### 3. STUDY DESIGN

This is a multi-center, double-blind, randomized, placebo-controlled, parallel-group study in patients with probable DLB who are either not receiving therapy for DLB or are receiving a stable regimen of standard therapy for DLB. The efficacy and safety of Intepirdine at doses of 70 mg and 35 mg daily will be evaluated over a 24-week treatment period. All subjects who are on stable doses of other therapies to treat cognitive deficits and/or hallucinations associated with DLB will continue to remain on them for the duration of the study.

Approximately 240 subjects will be randomized. The randomization ratio will be 1:1:1 (70 mg Intepirdine: 35 mg Intepirdine: placebo). Double-blind treatment will be administered as follows:

- 70 mg Intepirdine (Test therapy): Intepirdine 70 mg given as two tablets of intepirdine 35 mg
- 35 mg Intepirdine (Test therapy): Intepirdine 35 mg given as one tablet of intepirdine 35 mg and one tablet of placebo
- Placebo (Reference): Matching placebo, given as two tablets of placebo

The primary endpoint (UPDRS Part III) and the secondary endpoints (ADAS Cog 11 and CIBIC+) will be measured after 24 weeks of treatment. Study participation will last approximately 32 weeks: 0 to 4 weeks for Screening, a 2-week Single-Blind Run-In Period to evaluate baseline status, a 24-week randomized, double-blind, placebo-controlled Treatment Period and a 2-week Safety Follow-up Period for subjects who do not enter the extension study RVT-101-2002.

[figure not shown]
There will be weekly clinical assessments for the first two weeks of double-blind treatment, bi-weekly assessments thereafter until 12 weeks post-randomization and every six weeks thereafter. For certain visits (Visits 5, 7 and 9), subjects may have the option of whether to have assessments performed at the clinical study site or by a trained, visiting nurse in their own home.

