An independent Safety Monitoring Committee (SMC) will review interim safety data accumulated after approximately 30 subjects have completed 4 weeks of double-blind treatment and throughout the study at points specified in the SMC Charter. The SMC will provide their recommendation regarding the acceptability of reducing the visit frequency by omitting certain visits (Visits 5, 7 and 9) for both newly enrolled subjects and subjects active in the study at the time of the recommendation. Study enrollment will not be stopped or slowed to wait for SMC's recommendation and will proceed as planned with all visits until the SMC recommendation is made. Site will be formally notified of the SMC's recommendation regarding whether Visits 5, 7 and 9 can be omitted. [The meeting did occur and the SMC recommended Visits 5, 7, and 9 be omitted.]

After completion of Visit 12, the subject may be considered for enrollment in the extension study RVT-101-2002. If the subject does not enter the extension study, he/she will return for the Safety Follow-up Visit (Visit 13). Subjects who enter the extension study will not be required to complete Visit 13.

A study schema is shown in [Figure 1](#) and study scheduled assessments are presented in [Table 2](#).

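### SAP 10.8 reports QSO symptoms as raw by-visit occurrences although the gap between questionnaires runs from 7 to 42 days; the recall window needs correcting and the time course needs a rate

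*SAP*

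**What the plan says.** Protocol 8.3.2.8 sets the timing of the questionnaire ("At all visits, a short questionnaire will be used to assess the occurrence of" dizziness, fainting and falls) and gives no recall period. Protocol 10.4.5.5 plans descriptive results that "will be presented separately for each study visit and treatment group".

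SAP 10.8 lists the count item as "Number of times (since last minute", a look-back that cannot be meant literally. It then plans the presentation: "The number of occurrences of each symptom over time will be presented", and "These will be summarized and listed by treatment and visit", plus an any-time summary. It names no adjustment for the length of time a visit covers.

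SAP 10.8.1 adds a rate for falls only: falls summed over all treatment-period visits, divided by days on treatment, times 30. That rate is summarized by treatment and modelled without visit terms. Further analysis of each symptom is mentioned there, but no method is given.

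SAP 3 describes the visit spacing as "weekly clinical assessments for the first two weeks of double-blind treatment, bi-weekly assessments thereafter until 12 weeks post-randomization and every six weeks" thereafter. The same section records a change after the study had begun: "The meeting did occur and the SMC recommended Visits 5, 7, and 9 be omitted". The recommendation covers both new and active subjects.

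**The concern.** A count at a visit can be read against the count at another visit only if both cover the same length of time. Here they do not, and at some visits the length also differs between subjects, depending on whether they followed the full or the reduced schedule. SAP 10.8 was not adapted to this, although SAP 3 already records the committee's recommendation.

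The QSO is a named safety endpoint in both documents. Protocol 3.3 describes earlier repeat dosing at 70 mg as lasting up to 10 days, so the course of these symptoms over 24 weeks is new information. A by-visit table whose steps come from the calendar could be read as symptoms accumulating with treatment. It could also make a real early excess look flat within an arm.

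**Working it through.** **No planned figure to reproduce.** The documents give no expected rate, precision or event count for the QSO.

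**Intervals.** These are differences of the nominal days 0, 7, 14, 28, 42, 56, 70, 84, 126 and 168 (Time and Events Schedule, Table 2 in both documents), with and without Visits 5, 7 and 9 (Weeks 2, 6 and 10).

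| Week | Full schedule, days | Reduced schedule, days |
|---|---|---|
| 1 | 7 | 7 |
| 2 | 7 | – |
| 4 | 14 | 21 |
| 6 | 14 | – |
| 8 | 14 | 28 |
| 10 | 14 | – |
| 12 | 14 | 28 |
| 18 | 42 | 42 |
| 24 | 42 | 42 |

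Both columns sum to 168 days. On both, longest over shortest is 42/7 = 6. From Week 12 to Week 18 the step is 42/14 = 3 on the full schedule and 42/28 = 1.5 on the reduced one.

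**What recall does 10.8.1 need?** Summing visit counts and dividing by treatment days is valid only if the counts tile the treatment period, that is, if each covers the time since the previous visit. A fixed window longer than a 7-day gap would count some falls twice, and one shorter than a 42-day gap would miss some. No fixed window fits both.

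**Effect under since-last-visit recall.** Assume a constant Poisson rate r per 28 days. Over t days the mean count is r × t/28, and the chance of at least one event is 1 − exp(−r × t/28). The values of r are assumptions.

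| t, days | Mean count, r = 0.3 | At least one, r = 0.1 | At least one, r = 0.3 | At least one, r = 1.0 |
|---|---|---|---|---|
| 7 | 0.075 | 2.5% | 7.2% | 22.1% |
| 14 | 0.150 | 4.9% | 13.9% | 39.3% |
| 21 | 0.225 | 7.2% | 20.1% | 52.8% |
| 28 | 0.300 | 9.5% | 25.9% | 63.2% |
| 42 | 0.450 | 13.9% | 36.2% | 77.7% |

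- Mean counts rise 0.450/0.075 = 6-fold from Week 1 to Weeks 18 and 24, whatever r is.
- Yes/no incidence rises by 13.9/2.5 = 5.6, 36.2/7.2 = 5.0 and 77.7/22.1 = 3.5 times.
- The rise is in steps: flat over Weeks 4 to 12 (full schedule), over Weeks 8 to 12 (reduced) and over Weeks 18 to 24 (both).
- With r = 0.3 per 30 days, the unit in 10.8.1, incidence goes from 6.8% to 34.3%.

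**A real early excess.** Suppose r is 0.6 in the first week on drug and 0.3 afterwards. Week 1 incidence is 1 − exp(−0.6 × 7/28) = 13.9%. Week 4 on the full schedule is 1 − exp(−0.3 × 14/28) = 13.9%. The arm's own trend looks flat. Placebo at a steady 0.3 shows 7.2% at Week 1, so the comparison between arms at that visit still reveals the excess.

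**Mixing at Weeks 4, 8 and 12.** The number of subjects on each schedule is not given. If the share on the full schedule were 12.5% (30 of 240), the mean interval at Weeks 8 and 12 would be 0.125 × 14 + 0.875 × 28 = 26.25 days. At an assumed 50% it would be 21 days.

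**After adjustment.** Dividing each mean count by t and multiplying by 30 gives r × 30/28 at every visit on both schedules, for example 0.32 per 30 days at r = 0.3. The steps disappear.

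**The case against.** A reader might infer that these symptoms will rise with time on drug by construction. The documents do not support that. Since-last-visit recall is nowhere stated; the only wording in SAP 10.8 is unusable, and the falls sum supports it by inference alone. With a fixed recall window there would be no interval-driven rise in by-visit counts. All arms follow the same schedule, and the omission was recommended without regard to arm. Placebo would therefore show the same steps, and it stands beside each dose in the tables (SAP 7.3).

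A reader might also infer that falls are left without adjustment, or that an early excess would go unseen. Falls have the overall rate in 10.8.1. For symptoms recorded as adverse events, SAP 10.1 plans time to first onset in bins from first dose, and it allows Kaplan-Meier plots for falls. Safety analysis is descriptive (SAP 10), and no decision rule uses the QSO trend.

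These points stand, and they limit the finding. They do not remove it. The overall falls rate has no visit terms, dizziness and fainting have no specified rate, and neither the any-time summary nor the adverse-event bins correct the QSO time course that 10.8 sets out to show. If recall did turn out to be fixed, the by-visit counts would be comparable but the rate in 10.8.1 would be invalid. SAP text has to change either way.

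**Conclusion.** The point holds in a limited form. SAP 10.8 has an unusable recall window. If recall is since the last visit, its by-visit tables distort the within-arm time course in every arm. Under a constant rate, mean counts rise six-fold in steps from Week 1 to Weeks 18 and 24, and yes/no incidence rises about 3.5 to 5.6 times over the assumed rates of 1.0 down to 0.1 per 28 days. Weeks 4, 8 and 12 also mix interval lengths, to an extent that cannot be stated because the split between schedules is not given.

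The conclusion rests on the inferred recall window, nominal visit days and assumed constant rates. It does not extend to same-visit contrasts between arms, which are largely unaffected, or to the overall falls rate. This is a cheap improvement to a descriptive safety table and does not threaten the trial's main conclusions.

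**What to change.** 1. In SAP 10.8, correct the recall window of the count item so that it matches the questionnaire as administered.
2. If that window is since the last visit, keep the by-visit counts and add, for dizziness, fainting and falls alike, the rate in the unit of 10.8.1: events divided by days since the subject's previous QSO, times 30, with person-days shown.
3. Present this rate over Weeks 0–4, 4–8, 8–12, 12–18 and 18–24, which both schedules can fill, and fold the counts from Visits 5, 7 and 9 into those intervals. Use actual dates, since the ±5-day windows let a nominal 42-day gap run from 32 to 52 days.
4. Footnote the interval length on the yes/no by-visit table, including the two lengths at Weeks 4, 8 and 12.
5. If the window proves to be fixed, leave the by-visit table as it is and revise the falls rate in 10.8.1 instead.

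The cost is SAP wording, one derived variable (days since previous QSO) from visit dates already collected, and slightly longer tables. No new data are needed.

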#### **10.8.1. Falls as Reported from QSO**

The rate of falls per month will be analyzed using the data on fall occurrence that is collected at each visit in the Treatment Period via the Questionnaire for Signs of Potential Orthostasis.

Rate of falls per month = (total number of falls / duration (days)) x 30, where:

- Total number of falls = summation of falls over all visits in the Treatment Period (through Week 24)
- Duration of treatment (days) through Week 24 = (last dose date of double blind IP – first dose date of double blind IP) + 1

Incidence rate will be summarized by treatment. The incidence rate will be analyzed using the MMSE model methodology as described for the primary efficacy endpoint but without the ‘visit’ terms.

Additional analysis will be performed for each symptom by treatment, visit and overall

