### **6.6.2. Subject Withdrawal Procedures**

If a subject is prematurely discontinued from treatment with the IP, the investigator must make every effort to perform the evaluations scheduled for the Early Termination Visit ([Table 2](#)). In the case where the subject permanently discontinues study medication between scheduled clinic visits he/she should be recalled to the clinic as soon as possible and preferably within 7 days of stopping study medication for the Early Termination Visit.

**Lost to follow-up:** If a subject is lost to follow-up, every effort must be made by study center personnel to contact the subject, inquire about the reason for discontinuation/withdrawal, and follow up with any unresolved AEs/serious adverse events (SAEs). A minimum of 3 attempts at contact should be made and recorded in the subject's source documentation, with 1 contact being by certified letter. All measures taken to contact the subject and information received during those attempts must be documented.

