### 7.7.2. Visit Windows

Actual times will be used in the listings, individual concentration-time profiles, and in the calculation of PK parameters.

There are 4 study periods during this study:

- The **Screening Period** is defined as the period of time prior to the subject receiving the first dose of single-blind placebo run-in medication.
- The **Single-Blind (or Placebo) Run-In Period** is defined as the period from the first dose of single-blind run-in medication and ends on the last dose date of single-blind run-in medication. The assessments taken on the date of the first dose of randomized double-blind study medication will be assumed to have been completed before the first dose of double-blind study medication and will be slotted to this period.
- The **Double-Blind Treatment Period** starts on the date of first dose of randomized double-blind investigational product and ends on the last double-blind dose date +7 days. If the first dose of randomized investigational product is taken on the same day as the baseline assessments, it will be assumed that the baseline assessments were completed before the first dose of investigational product was taken.
- The **Post-Treatment Period**. For efficacy and health outcomes data, assessments are regarded as Follow-Up if the assessment occurred >7 days after the last dose date of randomized investigational product.

Data collected at assessment visits provide information of the status at that point in time (eg, efficacy measures, vital signs, laboratory parameters, etc.) and may provide biased results if the visit is attended early or late, in which case the subject will have received more or less treatment

than scheduled. For this reason, visits will be slotted with similar investigational product exposure.

Data will be phased first. All data that slots into the screening period will be assigned a visit of Screening. All data that occurs in Single-Blind Run-In Period will be assigned a visit of Run-in or Baseline depending on medication start/stop dates and data that slots into the Follow Up Period will be assigned a visit of Follow Up.

Post-baseline assessments from the Double-Blind Treatment Period data will be visit slotted according to the time intervals shown (Table 14) based on the days relative to the date of first dose of double blind investigational product (Day 1). Early withdrawal data that is assigned to Double-Blind Treatment Period will be slotted using the assessment windows.

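### For subjects who stop early, the SAP's falls-per-month rate counts falls over one time span and divides by another, which biases the expected rate up or down

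*SAP*

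**What the plan says.** SAP 10.8.1 defines "Rate of falls per month = (total number of falls / duration (days)) x 30". The numerator is "Total number of falls = summation of falls over all visits in the Treatment Period (through Week 24"). The denominator is ("last dose date of double blind IP – first dose date of double blind IP) + 1". The resulting rate is analysed with the primary-endpoint model, without its visit terms.

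Which QSOs enter the sum depends on other sections:

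- SAP 7.7.2 defines a Double-Blind Treatment Period. It "starts on the date of first dose of randomized double-blind investigational product and ends on the last double-blind dose date +7 days". Early-withdrawal data inside that period are slotted to visit windows. On later efficacy and health outcomes data the section says that "assessments are regarded as Follow-Up if the assessment occurred >7 days after the last dose date of randomized investigational product".
- SAP 7.7.2, Table 14: ET shares a row with the Week 26 follow-up visit. When two assessments fall in one window, the one nearer the target day is used for by-visit results.
- Protocol Table 2: the QSO is scheduled at ET, in a column outside the Treatment block.
- Protocol 6.6.2: a subject who stops between visits "he/she should be recalled to the clinic as soon as possible and preferably within 7 days of stopping study medication". Protocol 8.1 says such subjects are encouraged to attend.
- SAP section 3: Visits 5, 7 and 9 were dropped, leaving Weeks 1, 4, 8, 12, 18 and 24.

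The recall period for the number of episodes is printed in SAP 10.8 as the last minute. Protocol 8.3.2.8 gives none.

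**The concern.** A rate is unbiased when events and time come from the same interval. Here the events come from the days covered by QSOs and the time comes from the days of dosing. Nothing in SAP 10.8.1 aligns the two, says whether an ET QSO belongs to the Treatment Period, or deals with subjects who stop early.

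The mismatch can run either way. A counted ET QSO after the last dose brings in off-drug falls without adding days. A final QSO that is missed or excluded loses every fall since the last counted visit, while the dosing days stay in the denominator. The second case can follow from the protocol itself: section 7.6 calls for withdrawal after more than 7 consecutive days without drug, so if dosing never resumes the ET visit falls beyond last dose +7.

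Falls are singled out for analysis in this trial, and this is the SAP's only fall rate. The affected subjects are those who discontinue, some of whom may do so because of falls or dizziness. If early stopping differs between arms, the comparison of rates is distorted.

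**Working it through.** The documents give no fall rate, dropout rate or ET timing, so there is no stated figure to reproduce. The check needs two assumptions: each QSO covers the time since the previous completed one, and falls occur at a constant rate. Then

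expected SAP rate / true rate = days covered by counted QSOs / dosing days.

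Day 1 is the first dose and the Baseline QSO. With last dose on Day D there are D dosing days. An ET on Day D + 7 is D + 6 days after Baseline.

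| Last dose (Day) | ET 7 days later, counted | ET missed or not counted |
|---|---|---|
| 10 | 16/10 = 1.60 | 7/10 = 0.70 |
| 20 | 26/20 = 1.30 | 7/20 = 0.35 |
| 40 | 46/40 = 1.15 | 28/40 = 0.70 |
| 70 | 76/70 = 1.09 | 56/70 = 0.80 |
| 120 | 126/120 = 1.05 | 84/120 = 0.70 |
| 140 | 146/140 = 1.04 | 126/140 = 0.90 |

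The right-hand numerators are the last scheduled visits on or before stopping (Weeks 1, 4, 8, 12, 18). Between 6-weekly visits up to 125 − 84 = 41 days can be lost. An ET the day after the last dose gives D/D = 1, an exact match.

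**Completers.** With the last dose the night before Week 24, the ratio is 168/168 = 1. With the last dose 7 days before that visit, it is 168/162 = 1.04.

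**Missed intermediate QSO.** Under the recall assumption the next completed QSO picks up its falls, so nothing is lost. Only a missed final QSO matters.

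**Does a given subject's rate change?** Only if a fall occurs in the mismatched days, with probability 1 − exp(−rate × days/30). At an assumed 1 fall a month:

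- 6 extra days (Day 10, ET Day 17): 1 − exp(−0.2) = 18%.
- 36 lost days (Day 120, no counted ET): 1 − exp(−1.2) = 70%.

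**Across early stoppers.** This was simulated with the last dose uniform over Days 2 to 160, a counted ET 1 to 7 days later in a given share of stoppers, and 0.25 to 2 falls a month.

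| Share with counted ET | Spans differ | Rate actually changed | Mean ratio |
|---|---|---|---|
| 100% | 86% | 2.5% to 17% | 1.09 |
| 50% | 91% | 7% to 37% | 0.91 |
| 0% | 97% | 12% to 56% | 0.74 |

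**Arm level.** With a proportion d stopping early and completers at 1, the mean ratio is (1 − d) + d × (stoppers' mean ratio). At d = 30% this is 0.70 + 0.30 × 1.088 = 1.026 with every ET counted, and 0.70 + 0.30 × 0.741 = 0.922 with none. At d = 10% the figures are 1.009 and 0.974.

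**Between arms.** With equal true rates and 30% against 10% stopping early, the apparent rate ratio is 0.922/0.974 = 0.95 if no ET is counted and 1.026/1.009 = 1.02 if all are. If both arms lose 30% but all ETs count in one and none in the other, it is 0.922/1.026 = 0.90.

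**After the change.** Take a true rate of 1.00 a month and last dose on Day 40. With ET on Day 46 + 1 = 47 counted, the SAP rate is 1.15. With no ET it is 0.70. Dividing by the 46 or 28 observed days gives 1.00 in both cases.

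**The case against.** The strongest reply is that this matters little. SAP section 10 calls the safety analysis descriptive. Falls are also examined from adverse event data (SAP 10.1): the proportion who fall is compared by a CMH test, and time to first fall may be shown. QSO falls are tabulated by visit and at any time (SAP 10.8). None of these uses the dosing-day denominator. Protocol 6.6.2 also requires every effort to complete the ET evaluations. All of this stands, and it limits the importance of the point.

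The recall period is an inference, since the printed text cannot be used. That stands too, though a sum over visits makes sense only if each QSO picks up where the last one ended.

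Whether an ET QSO counts at all is ambiguous. SAP 10.8.1 names the Treatment Period, while SAP 7.7.2 defines the Double-Blind Treatment Period. Table 14 groups ET with follow-up, yet early-withdrawal data within last dose +7 are slotted to treatment windows. The one-per-window rule could also drop an ET QSO: on 59 of 160 possible ET days (37%), an earlier on-target visit shares the window. The SAP's all-data rule for any-time safety analyses may apply instead, but it does not say. The ambiguity decides which direction of bias occurs; no reading aligns the two spans in general.

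A reader might infer that the rate is wrong for most subjects who stop early. The documents do not support that. Most would probably have mismatched spans, but under the assumed ranges the realised rate changes for more than half only at 2 falls a month with no counted ET. Nor is it right that every missed QSO loses falls, or that completers are exactly unaffected.

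**Conclusion.** The defect is real and limited. For subjects who stop early, the expected rate is biased upward when an off-drug ET QSO within last dose +7 is counted. It is biased downward when the final QSO is missed, comes later, or is not treated as a Treatment Period visit. Individual ratios such as 1.60 and 0.70 are expected values; the larger upward ones need very early stopping and an ET near the 7-day limit.

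The average arm-level bias is probably modest, about 0.92 to 1.03 at an assumed 10% to 30% early stopping. It would be larger if early stoppers fall more often than others, which the constant-rate assumption excludes. The arm comparison suffers mainly if early stopping or ET attendance differs by arm. All sizes rest on since-last-QSO recall and on assumed stopping, attendance and fall rates. The definition is worth correcting before unblinding. It gives no reason to doubt the primary endpoint or the other fall analyses.

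**What to change.** Amend SAP 10.8 and 10.8.1:

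1. Correct the recall period to the time since the last completed QSO, after checking it against the form actually used.
2. State that all completed post-Baseline QSOs up to last dose +7, including ET, are counted, without one-per-window selection.
3. Replace the duration line with: Duration = days from the Baseline QSO (first dose) to the last counted QSO. Count falls over exactly those QSOs.
4. Use that duration in the falls analysis and report dosing duration separately.
5. Set the rate to missing for a subject with no counted post-Baseline QSO, who has no observed days.

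The cost is SAP wording and a small programming change, provided the form's recall matches; visit dates are already collected. There are two small downsides. Up to 7 off-drug days enter both numerator and denominator, as they already do in the on-treatment adverse event window. Falls first reported at an ET later than last dose +7 stay outside the rate.
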